Baseline for primary outcome	variable	All offences 6 months pre-randomisation
	measure (instrument, scale, source)	Local Police Database (LPD)
Baseline for secondary outcome	variable	Self-reported offences, emotional regulation, substance use frequency, psychological health and well-being, situational confidence, readiness to change, expectancies.

	measure (instrument, scale, source)	Baseline assessments of Self-Report Delinquency Scale (SRDS), Strengths and Difficulties Questionnaire (SDQ), Timeline Follow-Back (TLFB28), Warwick-Edinburgh Mental Well-being Scale (WEMWBS), Short Situational Confidence Questionnaire (SCQ-8), Readiness to Change Ruler (RR), Substance Use Expectancy Scale (SUE)
--	-------------------------------------	---

Randomisation

Randomisation strings are generated in advance for the research team by an independent, remote, secure randomisation service (Sealed Envelope Ltd). Strings are made up of random permuted blocks of size 4 and 6 with a random block distributed throughout the string to reduce predictability. Strings are stratified by age group (10-14 and 15-17 years) and site (Kent, Cornwall, Sefton and Wigan).

After consent has been provided and the baseline assessment complete the researcher accesses the randomisation service online, they provided the participant ID and stratification variables, and the system automatically provides an allocation.

The researcher has no access to the actual strings in advance of an allocation. After allocation the researcher informs *We Are With You* who contact the young person to deliver the allocated treatment.

All allocations are recorded independently and the allocation schedule is available for quality assurance purposes.

Participants

Participants are assessed for initial eligibility by police custody staff. Inclusion criteria included being aged 10-17 years inclusive and being found in possession of class B or C controlled drugs. Young people are excluded if they had been arrested for a sexual or serious violent offence, had a history of four or more previous offences or who had a substance severity that required specialist clinical intervention such as detoxification or medically assisted maintenance. All eligible participants are referred to *We Are With You* using a secure criminal justice email system.

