Rather than just assume the randomisation has worked, we will assess observed balance by comparing the means and distributions of the groups created by randomisation. If they are systematically different across those variables we observe – e.g. always larger / smaller in one group - then that would suggest the randomisation has not been successfully implemented. Baseline equivalence following randomization will be assessed by first looking at allocation by the two stratifying variables, site and age group, and then extending the comparison by key outcomes, mean offences at baseline and mean days using substances at baseline.

Baseline characteristics will be summarised by randomised group. Summary measures for the baseline characteristics of each group will be presented as mean and standard deviation for continuous (approximate) normally distributed variables, medians and interquartile ranges for non-normally distributed variables, and frequencies and percentages for categorical variables. Following CONSORT when comparing treatment and control groups we will not use statistical tests.

If there is a large imbalance between groups on a specific variable, then that variable will be included in the analysis model. If there are systematic differences across multiple variables that are indicative of failed randomisation then it would be necessary to explore alternative analysis methods to estimate treatment effects, such as instrumental variable models, using treatment allocation as the IV.

Missing data

The proportion of missing data and patterns of missingness will be examined for the primary outcome. Levels of missing data will be reported along with any systematic occurrences of missing data observed in the dataset.

We will explore the mechanism of missing data to establish whether the data can be considered missing completely at random or missing at random. For each treatment arm, participants will be grouped based on their dropout time, and means at baseline and each time will be examined to assess whether there are systematic differences between those who dropped out at specific time points and those who remained in the study.

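### Baseline differences that merely run the same way are weak evidence of failed randomisation and should not prompt a change of analysis

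*SAP*

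**What the plan says.** The SAP, under Imbalance at baseline, sets out how it will judge whether randomisation worked. The condition is "If they are systematically different across those variables we observe – e.g. always larger / smaller in one group", and the inference drawn is "then that would suggest the randomisation has not been successfully implemented".

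The comparison starts by "first looking at allocation by the two stratifying variables, site and age group", "then extending the comparison by key outcomes, mean offences at baseline and mean days using substances at baseline". Baseline characteristics are also summarised by arm. Significance tests are ruled out: "Following CONSORT when comparing treatment and control groups we will not use statistical tests".

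Two consequences follow in the same section. A large imbalance on a single variable leads to that variable being added to the model. For a wider pattern the SAP says: "If there are systematic differences across multiple variables that are indicative of failed randomisation then it would be necessary to explore alternative analysis methods". The example it gives is an instrumental variable model with allocation as the instrument.

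The Protocol, under Randomisation, describes permuted blocks of 4 and 6 from an independent service, stratified by age group and site. It says allocations are recorded independently and that "the allocation schedule is available for quality assurance purposes".

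**The concern.** Direction is the only content given to the idea of a systematic difference. No magnitude is required, the set of variables is not fixed, and no false-alarm rate is stated.

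Of the four variables named in the check, site and age group are stratifiers. Stratified blocks keep them close to balance, and site has no direction. That leaves two key outcomes on which direction could be informative, and two differences agree in sign easily by chance.

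At stake is the standing of the pre-specified intention-to-treat estimate. A chance pattern in a sound trial could be read as failed randomisation and used to question Eq. 1. Because the set of variables is open, that reading could be settled after the baseline table has been seen. Analysing with allocation masked, as the SAP plans, limits steering towards a preferred result. It does not lower the false-alarm rate.

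**Working it through.** **The plan's own figures.** The documents give no error rate for the balance check. The sample size used below does reproduce. For an effect of 0.3 SD, two-sided alpha 0.05 and 80% power, n per arm = 2(1.960 + 0.842)²/0.3² = 174.4, so 175 per arm and 350 in total. With the Protocol's 5% loss, 350/0.95 = 368.4, so 369, or 370 in equal arms of 185.

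**Two key outcomes, sound 1:1 allocation.** Each arm difference is symmetric about zero. With correlation ρ between the two variables, and the differences approximately bivariate normal,

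P(same direction) = 1/2 + arcsin(ρ)/π.

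The documents give no value for ρ. The Protocol's background says that substance use and offending are related, so a positive value is plausible, but the range here is an assumption.

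| ρ | P(same direction) |
|---|---|
| -0.3 | 0.403 |
| -0.1 | 0.468 |
| 0 | 0.500 |
| 0.1 | 0.532 |
| 0.3 | 0.597 |
| 0.5 | 0.667 |

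A simulation used 370 participants, 8 strata, blocks of 4 and 6, and assumed count distributions (offences negative binomial with mean 1; days binomial out of 28). It gave 49.5%, 55.2% and 59.5% at underlying correlations of 0, 0.2 and 0.4, with ties in under 1% of runs.

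**A wider set of variables.** For k variables with a common correlation ρ, where φ and Φ are the standard normal density and distribution function,

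P(all same direction) = 2∫φ(u) Φ(√ρ·u/√(1-ρ))^k du.

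| k | ρ = 0 | ρ = 0.3 | ρ = 0.5 |
|---|---|---|---|
| 2 | 50.0% | 59.7% | 66.7% |
| 4 | 12.5% | 28.1% | 40.0% |
| 8 | 0.8% | 10.4% | 22.2% |
| 10 | 0.2% | 7.3% | 18.2% |

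This model treats all scales as coded in one direction.

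**Two variants, by the same simulation (ρ 0 to 0.4).** If the age-group difference must also agree in direction with the two key outcomes, the rate is 23% to 28%. If the two key outcomes must share a direction and each differ by more than 0.1 SD, it is 5% to 11%.

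**Strength of the evidence on the two key outcomes.** The likelihood ratio for a broken against a sound allocation is P(pattern | broken)/P(pattern | sound). The numerator cannot exceed 1, so the ceiling is 1/0.500 = 2.0 at ρ = 0 and 1/0.597 = 1.68 at ρ = 0.3. At ρ = -0.3 it is 1/0.403 = 2.48.

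As an example, suppose a broken allocation shifts both variables by 0.2 SD. The standard error of a standardised difference is √(2/185) = 0.104, and 0.2/0.104 = 1.92. At ρ = 0 the pattern then appears with probability Φ(1.92)² + Φ(-1.92)² = 0.947, a ratio of 0.947/0.500 = 1.89. At ρ = 0.3 the probability is 0.951 and the ratio 0.951/0.597 = 1.59.

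**The case against.** The strongest reply is that the SAP offers same-direction differences only as an example, across whatever variables are observed, and says it will compare means and distributions. Size and shape would then be looked at as well as sign. The SAP's outcome table lists twelve instruments at baseline. Some of them, such as wellbeing and anxiety, would be expected to move in opposite directions unless recoded. On that reading false alarms are much rarer, as the ten-variable row shows. This stands as a limit on the size of the problem. It does not supply the missing threshold or the missing set of variables.

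Four stronger conclusions that a reader might infer are not supported:

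- **That the check misfires at least half the time.** This holds only for the two key outcomes and only if their correlation is not negative. The documents give no correlation.
- **That the pattern cannot distinguish a sound trial from a broken one.** A likelihood ratio of 1.6 to 1.9 is weak evidence, but it is not zero. Across many variables, agreement in direction would be less common by chance and could carry more weight.
- **That the intention-to-treat result would be replaced.** The SAP speaks of exploring alternatives after a judgement and does not withdraw Eq. 1. By the SAP's Eq. 3 and the pilot's 92% adherence, the instrumental variable estimate would be the intention-to-treat estimate divided by 0.92, about 1.09 times as large, and the SAP already plans it as the compliance analysis. That estimate also relies on allocation having been random, so it is no remedy if allocation failed.
- **That failure should be declared only when an audit of the log finds overrides.** A clean log cannot reveal selective enrolment, or allocations guessed from small blocks. Baseline comparison is one of the few signals of either.

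**Conclusion.** The point holds as a defect in a decision rule. The SAP reads direction as suggesting failed randomisation without fixing how many variables or how large a difference, and ties that reading to alternative analyses. The false-alarm rate could be anywhere from about 0.2% (ten uncorrelated variables) to 67% (the two key outcomes at a correlation of 0.5), depending on choices the SAP leaves open. On the two outcomes it singles out, the pattern is too weak to support a finding of failure.

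These figures assume sound 1:1 allocation, approximately normal arm differences, correlations that are assumed and not documented, and, for more than two variables, a common correlation. The practical harm is avoidable doubt about a sound primary result. Nothing in the documents shows that the result would be overturned.

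**What to change.** In the SAP section on imbalance at baseline:

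1. Remove same-direction differences as a sign of failed randomisation, and remove the sentence that moves to alternative methods such as an instrumental variable model with allocation as the instrument.
2. State that Eq. 1, by allocated arm, remains the primary analysis whatever baseline pattern is seen. Report any adjustment for further imbalanced variables as a sensitivity analysis.
3. Check implementation mainly by reconciling the independent allocation record described in the Protocol with the arm notified to the provider and the arm analysed, participant by participant.
4. Keep the baseline table as a descriptive prompt to investigate recruitment and allocation, including selective enrolment, and not as proof of failure.

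The cost is a wording change and a short reconciliation against a record that already exists. The small downside is that baseline patterns no longer trigger a change of primary analysis.

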We will assess adherence by recording attendance at each element of the intervention and the control. For those in the intervention group we will assess fidelity by randomly recording 20% of brief intervention sessions stratified by age group, interventionist and site and independently score these using the Behavioural Change Counselling Index (BECCI; (Lane, 2002)). We will ask participants in the intervention arm to complete the short revised therapeutic alliance scale for children after the second intervention session (TASC-r; (Shirk and Saiz, 1992)). There is emerging evidence that the perceptions of interventionists play a key role in the quality of intervention delivered, particularly in terms of their perceived role legitimacy and self-efficacy, both targets of training and ongoing supervision. In order to assess these perceptions, we will ask interventionists to complete the Drug and Drug Using Populations Perceptions Questionnaire (DDPPQ; (Connors et al., 2019)) just prior to training and again 6-months after being trained.

Analysis

In the overall analysis, data from the internal pilot and efficacy study will be combined and analysed blind to group allocation. The efficacy analysis will be conducted and presented in accordance with the CONSORT guidelines. The validity of randomisation will be explored by presenting measures of central tendency and estimates of precision for continuous variables,

and proportions for categorical variables broken down by allocation arm and stratification factors.

The primary outcome is the frequency of non-violent offences at 6-months post-randomisation, and this will be conducted as an analysis by treatment allocated (ITT) and will include all available data maintaining participants as members of their allocated group. Prior to analysis we will conduct a series of diagnostic tests and assess the underlying assumptions prior to choosing an appropriate and statistically rigorous regression model.

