[name]; Intervention delivery Kent.

[name]; Intervention delivery Cornwall.

[name]; Intervention delivery Sefton.

[name]; Intervention delivery Lancashire.

Risks

Our experience of similar studies has enabled us to develop and pilot several risk mitigations strategies. We have identified the following key risks:

1. Lack of engagement by stakeholders. We plan on actively engaging with all stakeholders to ensure the importance of the project is recognised. We aim to visit all sites early on and plan on engaging with staff at all levels in the partner organisations (LOW).

2. Potential contamination. As a randomised controlled trial, the potential for contamination is low. The design of the standardised control group, delivered by staff not involved in delivering the intervention, will address any potential for contamination. All follow-ups will be conducted blind to baseline allocation (LOW).

3. Poor recruitment. We have extensive experience of working with marginalised populations. In addition to clear referral and recruitment strategies we will ensure recruitment is constantly monitored to identify emerging issues, reduce barriers to participation by using few inclusion criteria and minimising exclusion criteria, providing clear information, and ensuring participants are clear on what the trial entails. Our previous experience with a similar population recruited 80% of those participants considered potentially eligible, in our pilot study we recruited 80% of those eligible. (LOW).

4. Poor adherence to follow-up. As our primary outcome measure is not participant assessed this issue relates in the main to the collection of secondary and process measures. In our previous studies with similar populations we have met, and exceeded, our target follow-up rate of 70% at 6-months and in our pilot study we followed up 88% across both groups. We have developed several follow-up strategies including multiple contact details, details of contactable others and ensuring participants are recompensed for the time spent engaging in follow-up assessments (LOW).

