To avoid loss of efficiency, missing outcome values will be imputed using multiple imputation for chained equations. This approach will only be undertaken if the proportion of missing data is greater than 5% and less than 40%. Where there is less than 5% missing data, the proportion of missing data is considered negligible and missing observations will be excluded. Multiple imputation methods perform less well when the amount of missing data is substantial, if more than 40% of the primary outcome data are missing the assumptions underlying the primary analysis are less plausible. Data will be analysed without imputation and the interpretative limitations of the trial data will be discussed in the results section.

An imputation model, containing all potential prognostic baseline covariates will be used. The number of imputations will be dependent on the amount of missing data, as a minimum the number of imputations will be derived to ensure at least 96% statistical efficiency (RE) according to the formula below (Eq. 2), where λ is the fraction of missing values and M is the number of repetitions.

Eq. 2

$$RE = \left(1 + \frac{\lambda}{M}\right)^{-1}$$

The statistical model and assumptions made in the analysis of the primary outcome will also be implemented in the multiple imputation procedures. If it is suspected data is missing not at random or the pattern of missing data is associated with trial allocation, sensitivity analysis will be performed using a pattern mixture approach with mixed modelling and multiple imputation to compare the sensitivity of conclusions to varying assumptions about the missing value mechanism. All available data from baseline to the time of dropout will be included in the sensitivity analysis using a repeated measures mixed effects model.

Compliance

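### The imputation model names no post-randomisation predictor, although police offences over the same six months are held for participants who miss the month-6 interview; OFF6 should be named as an auxiliary variable

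*SAP*

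**What the plan says.** The SAP, Missing data, plans that "missing outcome values will be imputed using multiple imputation for chained equations" when more than 5% and less than 40% of the data are missing. On the content of the model it says "An imputation model, containing all potential prognostic baseline covariates will be used", and then "The statistical model and assumptions made in the analysis of the primary outcome will also be implemented in the multiple imputation procedures". The covariates in Eq. 1 are allocation, offences in the six months before randomisation, age group, site and pilot/efficacy study. All are fixed at or before randomisation. Neither document names a post-randomisation variable as a predictor.

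The section is framed on the primary outcome: "The proportion of missing data and patterns of missingness will be examined for the primary outcome". Its use for secondary outcomes has to be inferred from the general phrase about missing outcome values and from SAP, Secondary outcome analysis, which says those analyses will resemble the primary one.

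The Protocol, Risks item 4, says of loss to follow-up: "As our primary outcome measure is not participant assessed this issue relates in the main to the collection of secondary and process measures". The SAP Introduction reports 88% month-6 follow-up in the pilot and the primary outcome available for everyone. SAP, Primary outcome analysis, keeps withdrawn participants in the ITT dataset. The Protocol, Compliance, adds "We will assess adherence by recording attendance at each element of the intervention and the control".

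Both documents plan pattern-mixture sensitivity analyses. Protocol, Analysis, states them without condition. The SAP runs them if data are suspected to be missing not at random or if missingness is associated with allocation.

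**The concern.** A young person who cannot be reached at month 6 usually still has a police record for the same six months. Re-offending is a plausible predictor both of being lost and of self-reported delinquency, substance use and SDQ scores. An imputation model without it treats a participant re-arrested and then lost as exchangeable with one who has the same arm and baseline and no arrest.

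The outcomes exposed include SRDS and SDQ, which the documents mark as the funder's core outcomes. They also include TLFB, for which Protocol, Secondary outcomes, collects only a single frequency item at baseline, so baseline prediction is likely to be weaker there. Assessments take place only at baseline and month 6. The repeated-measures model in the SAP's sensitivity analysis therefore adds nothing after baseline for someone who misses the interview.

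**Working it through.** **1. The plan's own figure.** Per arm, n = 2(1.960 + 0.842)² / 0.3² = 174.4, so 175, or 350 in total, as stated. Allowing for 5% loss, 350 / 0.95 = 368.4, so 369 against the stated 370. The total of 370 is used below.

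**2. Where imputation would apply.**
- Police outcome: 100% available in the pilot, below the 5% trigger, so no imputation is expected.
- Interview outcomes at the pilot rate: 370 × 0.12 = 44 missing, about 22 per arm.
- Interview outcomes at the 70% target: 370 × 0.30 = 111 missing.

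Both interview rates lie inside the 5% to 40% band.

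**3. Standard error of the arm difference, in SD units.** Unadjusted, √(4/(370 × 0.88)) = 0.111 and √(4/(370 × 0.70)) = 0.124. With an assumed baseline-outcome correlation of 0.5, √(4 × 0.75/325.6) = 0.096 and √(4 × 0.75/259) = 0.108. So the range is about 0.10 to 0.12.

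**4. Bias by hand.** Assume, since the documents give no figure, that the odds of loss double per SD of offending in one arm only. Assume also that offending correlates 0.2 to 0.5 with the secondary outcome given baseline. To first order, completers in that arm have mean offending shifted by −ln(2) × (fraction lost). The bias is that shift times the correlation:
- 12% loss: 0.693 × 0.12 = 0.083; times 0.2 to 0.5 gives 0.017 to 0.042 SD.
- 30% loss: 0.693 × 0.30 = 0.208; times 0.2 to 0.5 gives 0.042 to 0.104 SD.

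These are slightly high, because baseline explains part of the variation in both variables.

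**5. Bias by simulation.** The same assumptions were run with 2,000,000 records per scenario and a true effect of 0 or −0.30 SD. Baseline imputation was taken at its large-sample limit, regression of completers on arm and baseline. The table gives absolute bias in SD units.

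| Loss mechanism | 12% lost | 30% lost |
|---|---|---|
| Same in both arms, intervention does not change offences | about 0 | about 0 |
| Same in both arms, intervention cuts offences by 0.3 SD | 0.003 to 0.006 | 0.004 to 0.010 |
| One arm only, correlation 0.2 | 0.013 to 0.016 | 0.032 to 0.034 |
| One arm only, correlation 0.3 | 0.020 to 0.022 | 0.049 to 0.053 |
| One arm only, correlation 0.5 | 0.035 to 0.037 | 0.080 to 0.086 |
| Any of these, with OFF6 and OFF6-by-arm in the imputation | at most 0.002 | at most 0.002 |

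Loss of re-offenders from the control arm shrinks an apparent benefit; loss from the intervention arm inflates it. As a share of a 0.30 SD effect, the one-arm extremes are 0.037/0.30 = 12% and 0.086/0.30 = 29%. As a share of the unadjusted standard error they are 0.037/0.111 = 0.33 and 0.086/0.124 = 0.69.

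**6. At the trial's size.** A check with n = 370 and 3,000 runs assumed that loss follows re-offending in one arm (33% with any offence, odds of loss about four times higher) and a latent correlation of 0.3 to 0.5. At 12% loss, baseline imputation gave a bias of 0.017 to 0.031 SD with a sampling SD of about 0.096. Adding OFF6 moved root mean squared error from 0.098–0.100 to 0.095–0.096 and left the sampling SD unchanged. At 30% loss, root mean squared error fell from 0.113–0.125 to 0.106.

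**The case against.** A reader might infer that the SAP has chosen a baseline-only model for participants lost to interview. It does not say so. It says what the model contains, not that nothing else may enter, and the section is written around the primary outcome. For a missing police count, OFF6 cannot be its own predictor. What the text shows is that imputation of secondary outcomes is under-specified and that the one description given omits a useful variable.

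A reader might also infer that the secondary results are left unprotected. The pattern-mixture analyses are a real safeguard, and arm-related missingness is one of the SAP's triggers for them. They do not name police offences, so they do not replace OFF6 in the main imputation. They remain the only protection against loss driven by unrecorded offending or by substance use itself.

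The planned set of baseline covariates is broader than the secondary analysis models. Prior offences, ACEQ, GAD-7, PHQ-A and BFRS could carry some information about re-offending. In a check, a baseline predictor correlated 0.4 with latent offending removed only a small part of the bias, so this objection stands only in part.

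The sizes rest on assumption. No document reports loss by offending or by arm, and adherence was 92% in the pilot. The simulations generated loss from recorded offences, so recovery with OFF6 follows by construction. There is also almost no efficiency gain at 12% loss, so the case rests on bias. The objection stands on both counts.

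**Conclusion.** The concern holds in a limited form. The stated imputation model names no post-randomisation predictor, while a relevant one should be held for nearly everyone who misses the interview.

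The avoidable bias is 0.013 to 0.037 SD at the pilot's 12% loss and 0.032 to 0.086 SD at 30%. This requires loss to follow re-offending in one arm only, with odds doubling per SD and a conditional correlation of 0.2 to 0.5. In every scenario it is below one standard error. When both arms share the mechanism it is at most 0.010 SD.

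The documents do not support the stronger readings that secondary results will be biased, that imputing with OFF6 corrects all informative loss, or that it buys meaningful precision. The primary outcome is not affected. This is a low-cost improvement, best pre-specified so that the choice of auxiliary variables is not made after the data are seen.

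**What to change.** In SAP, Missing data, state that:
- multiple imputation applies to each secondary outcome that meets the 5% to 40% rule;
- the chained-equations model contains allocation, the baseline covariates and OFF6 (police-recorded offences to month 6) as an auxiliary variable;
- an OFF6-by-arm term is included, or imputation is run separately by arm, where numbers allow (about 22 lost per arm at 12%).

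Sessions attended, and other observed month-6 measures for partial interviews, are optional further auxiliaries. Their benefit was not tested here, and other month-6 measures do not help when the whole interview is missed. The analysis models do not change, and the pattern-mixture analyses stay.

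The cost is wording only, since the police data are already collected for the primary outcome. The one constraint is that secondary imputation must wait for the linked police extract. The Protocol timeline ends that extraction on 30/03/25, a month before analysis closes on 30/04/25.

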Proportion referred who are eligible	70%	50%	40%
Proportion eligible who consent	70%	50%	40%
Proportion eligible who adhere	80%	60%	40%
Proportion followed-up (secondary)	80%	70%	60%

Table 1: Pilot trial progression criteria (green go, amber review, red stop).

All these criteria were met; 93% of those referred were eligible, 80% of these consented, 92% adhered to all the intervention, 88% were followed-up at month 6, the primary endpoint, and the primary outcome was available for 100% of participants.

The qualitative analysis found the intervention was considered acceptable to all stakeholders, young people, interventionists, and the police. The qualitative analysis found no substantial hindrances to the implementation of the Reframe intervention, but it did highlight some areas where improvements to referral processes could be made. These included raising awareness within the police and streamlining referral pathways.

Interventions

Participants were assessed for initial eligibility by police custody staff. Inclusion criteria included being aged 10-17 years inclusive and being found in possession of class B or C controlled drugs. Young people were excluded if they had been arrested for a sexual or serious violent offence, had a history of four or more previous offences, were in possession of a Class A substance or who had a substance severity that required specialist clinical intervention such as detoxification or medically assisted maintenance. All eligible participants were referred to we Are With You using a secure email system.

Staff at *With You* established whether potential participants were interested in participating in the trial and if they were they provided a paper or email copy of the information sheet and passed their contact details to the trial research staff. Trial research staff contacted the young person and checked they understood the information sheet and answered any queries. If the young person was considered Gillick competent full signed consent was taken. If a young person was not considered Gillick competent signed assent was taken from the young person and formal consent taken from a primary carer.

Immediately after consent the young person completed the baseline outcome measures and was immediately randomised using a remote, independent secure randomisation service to business as usual or intervention. We are with you were informed of the allocation and delivered the treatment.

Intervention Group

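### The 96% relative-efficiency rule allows as few as 2 to 10 imputations, so a borderline result for an imputed (mainly secondary) outcome could depend on the random seed

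*SAP*

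**What the plan says.** The SAP's Missing data section uses chained-equations multiple imputation for missing outcome values within a stated band: "This approach will only be undertaken if the proportion of missing data is greater than 5% and less than 40" per cent. No single value of M is given. Instead, "The number of imputations will be dependent on the amount of missing data", and "as a minimum the number of imputations will be derived to ensure at least 96% statistical efficiency", using Eq. 2, RE = (1 + λ/M)⁻¹, in which λ "is the fraction of missing values and M is the number of repetitions". Neither document gives a value of M, a higher floor, a Monte Carlo error criterion or a seed.

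On expected missingness, the SAP Introduction reports that in the pilot "88% were followed-up at month 6", with the primary outcome available for everyone. Under Risks (item 4), the protocol refers to "our target follow-up rate of 70% at 6-months" in the team's previous studies, and says that this target was met and exceeded. The SAP's section on confidence levels and p-values commits to 95% intervals and a two-sided 0.05 threshold.

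**The concern.** A pre-specified analysis should give the same answer whoever runs it. With few imputations, the pooled estimate, the between-imputation variance and the degrees of freedom all carry simulation noise, so the interval and p-value change with the seed. Relative efficiency speaks only to the first of these, as variance lost in the point estimate. A target of 96% sounds demanding, but it is met by two or three imputations at modest missingness.

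An analyst who used M = 3 at the pilot's level of loss would comply fully with the SAP. For a result near 0.05, the same data could then be reported as significant or not. Because M and the seed are both open, either could also be chosen after results are seen.

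**Working it through.** **Inputs.** RE ≥ 0.96, Eq. 2 and the 5–40% band (SAP, Missing data). Pilot follow-up of 88%, so λ = 0.12, and the green progression threshold of 80%, so λ = 0.20 (SAP, Introduction and its Table 1). The 70% target of earlier studies, so λ = 0.30 (protocol, Risks). N = 370 (both documents).

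**Step 1: solve Eq. 2 for M.** 1/(1 + λ/M) ≥ 0.96 gives λ/M ≤ 1/0.96 − 1 = 0.0417, so M ≥ 24λ, rounded up.

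| λ | 24λ | Minimum M | RE at M | RE at M − 1 | √(λ/M) |
|---|---|---|---|---|---|
| just above 0.05 | 1.2 | 2 | 0.976 | 0.952 | 0.16 |
| 0.12 | 2.88 | 3 | 0.962 | 0.943 | 0.20 |
| 0.20 | 4.8 | 5 | 0.962 | 0.952 | 0.20 |
| 0.30 | 7.2 | 8 | 0.964 | 0.959 | 0.19 |
| just below 0.40 | 9.6 | 10 | 0.962 | 0.957 | 0.20 |

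**Step 2: Monte Carlo noise at the floor.** The last column approximates the between-seed SD of the pooled estimate in standard errors, taking the fraction of missing information as about λ. By Step 1 it cannot exceed √0.0417 = 0.20. For a result at z = 1.96, two such SDs span 1.96 ± 1.96 × 0.20, that is 1.57 to 2.35, or p from about 0.12 to 0.02. This leaves out the further noise in the estimated standard error.

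**Step 3: simulation.** Assumptions: N = 370, 1:1 allocation, continuous outcome, baseline correlation 0.5, outcomes missing completely at random, normal-regression imputation, Rubin's rules with small-sample degrees of freedom, 60 datasets with 200 seeds each. The true difference of 0.22 SD was chosen to put results near p = 0.05. The last two columns cover only the 16–24 borderline datasets per setting (median p between 0.02 and 0.10).

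| λ | M | Seed SD / SE | Interval width, 95th/5th percentile | p, 5th–95th percentile over seeds | Two seeds disagree on p<0.05 |
|---|---|---|---|---|---|
| 0.06 | 2 | 0.171 | 1.29 | 0.023–0.113 | 33% |
| 0.06 | 20 | 0.055 | 1.04 | 0.040–0.061 | 6% |
| 0.12 | 3 | 0.197 | 1.35 | 0.021–0.127 | 36% |
| 0.12 | 50 | 0.049 | 1.04 | 0.040–0.060 | 9% |
| 0.30 | 8 | 0.190 | 1.37 | 0.017–0.112 | 37% |
| 0.30 | 100 | 0.055 | 1.08 | 0.038–0.063 | 9% |
| 0.39 | 10 | 0.194 | 1.43 | 0.016–0.124 | 39% |
| 0.39 | 100 | 0.062 | 1.10 | 0.036–0.066 | 14% |

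The simulated seed SDs agree with Step 2.

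**Step 4: rates not conditioned on a borderline result.** At 0.22 SD, two seeds disagreed in 12–15% of all datasets at the floor, but that effect was picked to sit near the threshold. Under the same N, correlation and missingness assumptions, they disagreed in about 3% of datasets with no effect and 8–9% at 0.3 SD; a separate run gave about 7% (λ = 0.12, M = 3) and 10% (λ = 0.30, M = 8) at 0.3 SD. Rejection under no effect stayed at 4–5%.

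**Step 5: can the primary outcome reach the trigger?** More than 5% of 370 means at least 19 participants (19/370 = 5.1%). The gap between 370 recruited and 350 needed is 20 (20/370 = 5.4%), so using all of it would just cross the trigger, with a floor of M = 2. Pilot availability was 100%.

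**The case against.** The strongest reply is that Eq. 2 sets a floor. The SAP asks for at least 96% and allows more, so a reader who infers that results will depend on the seed goes further than the text. The instability arises only if the minimum, or something close to it, is used. That stands, and the point is conditional on it. Still, nothing in the SAP requires more.

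A reader might also infer that the primary result is at risk. The documents do not support this: the outcome comes from police records, was complete in the pilot, and is not imputed below 5% missing.

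Use of the rule for secondary outcomes is an inference. The Missing data section speaks mainly of the primary outcome, the Secondary outcome analysis section does not mention imputation, and the protocol's Analysis section places multiple imputation among the sensitivity analyses. However, the SAP imputes missing outcome values without restriction and says that secondary outcomes will be analysed much as the primary is. The reading is plausible but not explicit.

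A reader might suspect more false positives. There are none to speak of, because the combining rules allow for finite M.

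The 30% case is pessimistic, given a pilot loss of 12% and earlier studies that beat their 70% target. The noise is also towards the upper end: adding one further predictor (assumed correlation 0.5) to the imputation model lowered it from about 0.19 to 0.16 standard errors, and the SAP plans a broad set of baseline predictors.

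Finally, it is tempting to blame the definition of λ as missing values rather than missing information. Changing it would not help: where covariates predict well, missing information is the smaller fraction, and the floor would be no higher.

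**Conclusion.** The concern holds as a matter of reproducibility, with a slight loss of precision. The 2-to-10 range follows from the SAP's own formula and rests on no simulation assumption. If the minimum is used, Monte Carlo noise is about 0.16–0.20 standard errors, and a p-value near 0.05 typically ranges from about 0.02 to 0.11–0.13 over the central 90% of seeds. The precision cost is small: variance is inflated by at most 1/0.96, about 4%.

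Clear results would not change. Over all datasets, two seeds would reach different significance verdicts in about 3% of cases with no effect and 8–9% at 0.3 SD. These rates depend on the assumed baseline correlation of 0.5, data missing completely at random and a continuous outcome.

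The practical exposure is in the self-reported secondary outcomes, including SRDS and SDQ (the funder's core outcomes) and TLFB, where the pilot's 12% loss gives a floor of three imputations. The documents do not support a claim that the primary conclusion or the type I error is threatened.

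**What to change.** In the SAP's Missing data section, replace the 96% relative-efficiency minimum with a larger fixed minimum, for example 100 imputations (50–100 gives similar stability). Pre-specify and record the seed. Report the Monte Carlo error of the estimate and p-value for each imputed outcome, and raise M if that error is material. The last clause is needed because, at 39% missing, two seeds still disagreed in 14% of borderline datasets with M = 100. The same sentence should say whether the rule covers secondary outcomes. The cost is one SAP sentence and negligible computing for 370 participants; no data collection or design element changes.
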